## STATISTICAL ANALYSIS PLAN:

The estimated incidence of PPD in U.S. American women is 20%, commensurate with estimates of institutional rates of PPD at Magee-Womens Hospital.36 As a pilot, we will target 10% of the sample required for a full study. The primary outcome is risk for PPD, measured by EPDS score at the 6-week postpartum visit. A sample of 394 participants, 197 in each group, will have 80% power to detect a 10% reduction in PPD symptoms at a significance level of 5% (two-tailed). With an optimistic estimated attrition of 15%, a full trial would aim to enroll 454 participants, 227 in each group. For this pilot we will target a sample of 23 patients in each group (total 46), to yield 10% of the full study sample. Given a yet unknown attrition rate, we estimate that study procedures in a maximum of 60 participants in each group will be the maximum number of participants necessary to establish a clear protocol. We will review and refine the protocol every 5 patients until no further changes to the protocol are made over 5 consecutive participants. We will prospectively gather data on screening eligibility, consent and decline rates, crossover rates, and provider and subject feedback.

Linear regression will be used to examine the relationship between EPDS scores and treatment group, both over time in participants and by group. The relationship between pain and EPDS will also be examined using linear regression. T-tests, linear regression, and chi-squared tests will be used, where appropriate, to examine the relationships between treatment group and pain, infant attachment, infant development, and breastfeeding.

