## CSE vs. Epidural for Postpartum Depression NCT03022526 July 15, 2020

## STUDY PROTOCOL:

The clinical procedure that will be used for research purposes is labor epidural analgesia initiation by combined spinal-epidural (CSE) or epidural (E).

Study participants, prior to enrollment, will have already made a decision for themselves to use labor epidural analgesia to manage pain during labor (decision made is one eligibility criteria). The study intervention, CSE or E, are both commonly used techniques in the initiation of epidural analgesia, but currently the utilization of one or the other of these strategies is left to the discretion of the anesthesia clinician and is dictated primarily by clinician preference. Thus an RCT will address this level of bias. Both CSE and E can be considered the standard of care for any laboring woman requesting labor epidural analgesia.

BASELINE: At the first encounter, an assessment will include measurements of depression (EPDS), anxiety (STAI inventory), resiliency (ER 89), pain catastrophizing (PCS), perceived social support (MSPSS) and pain (BPI-long form). For women recruited at the 3rd trimester visit, Quantitative sensory testing (QST) will be performed. The pain sensitivity test will involve the use of a small pad attached to the participant's arm. The thermal device will gradually heat up from the moment the participant feels the heat until the pain sensation becomes uncomfortable; the participant is instructed to tell investigators when to discontinue the test at the first moment of discomfort, at which time the test is stopped. The pain sensitivity test also includes pressure devices to assess pressure pain. These devices are widely and commonly used in clinical pain research. From these test, we will determine the participant's sensitivity profile which we will use in our study analysis.

To enhance recruitment, we will also approach women in early labor who have not yet received an epidural after consultation with their bedside nurse and once it has been established that they meet eligibility criteria. These women will answer the aforementioned baseline surveys but will not participate in QST.

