Upon hospital admission for labor and delivery: confirmation of term (>/= 37 weeks) planned vaginal delivery will occur. The participant will be randomized to one of two groups: combined spinal-epidural (CSE) or epidural (E). Randomization will occur by block allocation. At the moment of patient request for labor epidural analgesia, one sealed and opaque envelope containing the next assignment group will be opened. The envelopes will be located in a designated location in the anesthesia workroom of the birth center, and thus no delays in the laboring person's ability to receive the requested epidural is anticipated. Should any delay occur for any reason, no randomization will occur and the patient will receive the epidural per routine request and clinical flow. Initiation of each labor analgesic strategy will be standardized to minimize variability of analgesia, and is outlined on the study figure attached. Management of breakthrough pain will be standardized and will occur by the strategy outlined on the study figure attached ("supporting documentation").

Throughout labor, pain will be assessed hourly using 100mm visual analog scales for both pain intensity and pain unpleasantness. Regardless of onset of labor (spontaneous or induction), hourly assessments are required to measure with accuracy and density the change in pain that is

CSE v. Epidural for Postpartum Depression

experienced over time for women in labor, in response to both the progress of labor and any changes in response to medications via the epidural infusion. For the entire labor, labor variables will be recorded, including sterile vaginal exam (SVE) at the time of epidural request, duration of labor (time from admission to unit until time of delivery), number of manual epidural supplemental doses, total dose of local anesthetic and epidural opioid required, and the outcome of labor -- both maternal (normal spontaneous vaginal delivery, instrumental delivery, cesarean delivery, perineal lacerations, total oxytocin dose requirements) and neonatal (sex, Apgar scores, need for resuscitation, need for neonatal ICU). Study procedures will continue should the need arise for a cesarean delivery or if there are any other complications to the pregnancy/fetus.

Postpartum measurements will be made as follows:

Postpartum day 0-2: Within 2 days we will measure co-variates of pain (BPI short), breastfeeding (yes/no) and perceived stress (PSS).

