At 6 weeks, we will measure the primary outcome of EPDS score as well as co-variates including pain (BPI short), maternal infant attachment (MPAS), parenting self-efficacy (PMP-SE), child development (ASQ-3), and breastfeeding (yes/no) (i.e. "Are you currently breasfteeding? Yes or no.") A margin of 7 days around the 6 week postpartum mark will be allowed for the patient to respond.

At 3 months, we will assess breastfeeding (Y/N), Depression (EPDS), Pain (BPI – Short Form), Mother-infant attachment (MPAS), Parenting self-efficacy (PMP-SE), Child development (ASQ-3). A margin of 7 days around the 3 month postpartum mark will be allowed for the patient to respond.

Should a participant not respond to follow-up surveys at the specified time, we will exclude their data from analysis; depending upon the volume and nature of such missing data, we reserve the ability to impute missing data if MAR or MNAR.

Interactions with participants will occur in person, electronically (email), or by phone. Investigators will consent participants to retain the ability to re-contact participants at a future date for follow-up questions.

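### The SAP names linear regression for EPDS followed over time, but gives no method for the correlation between repeated scores from the same woman

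*Combined protocol and SAP*

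**What the plan says.** The Study Protocol collects EPDS on three occasions.

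- **Baseline:** "At the first encounter, an assessment will include measurements of depression (EPDS". Women recruited in early labor complete the same baseline surveys and omit only the sensory testing, so a pre-randomization EPDS is planned for everyone.
- **6 weeks:** "we will measure the primary outcome of EPDS score".
- **3 months:** "At 3 months, we will assess breastfeeding (Y/N), Depression (EPDS".

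The Statistical Analysis Plan fixes the primary time point: "The primary outcome is risk for PPD, measured by EPDS score at the 6-week postpartum visit". For EPDS and treatment it gives one sentence of method: "Linear regression will be used to examine the relationship between EPDS scores and treatment group, both over time in participants and by group". The only other methods it names, for other outcomes, are t-tests and chi-squared tests. Neither part of the document mentions a mixed model, GEE, robust standard errors, a covariance structure, change scores or adjustment for baseline EPDS.

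On size, the SAP says: "For this pilot we will target a sample of 23 patients in each group (total 46". It allows up to 60 per group.

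**The concern.** Ordinary linear regression assumes that its rows are independent. Two EPDS scores from one woman, taken at 6 weeks and 3 months, are not. The SAP commits to a question about the course of EPDS within women and names a method that, applied literally to stacked scores, gives wrong standard errors.

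The error runs in opposite directions for the two natural contrasts. The standard error of the group effect, averaged over visits, is too small, so a group difference is declared too often. The standard error of the group-by-time effect is too large, so that test is too conservative. A reader of the results could not correct both with one rule of thumb. At stake is how the pilot's EPDS trajectory results are read.

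**Working it through.** **The plan's own figure.** The SAP gives no figure for the over-time analysis. Its sample size is 197 per group for 80% power at two-sided 5%, with PPD at 20%. Reading the 10% reduction as 20% versus 10%, the unpooled two-proportion formula gives

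(1.960 + 0.842)² × (0.20×0.80 + 0.10×0.90) / 0.10² = 196.2, rounded up to 197.

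This reproduces the stated number. It rests on one 6-week comparison with one value per woman, so nothing below changes the sample size.

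**Inputs.**
- Two postpartum scores per woman, at 6 weeks and 3 months (Study Protocol).
- 23 women per group (Statistical Analysis Plan).
- Nominal two-sided 5%. The SAP sets this level for the full-trial sample size; it is assumed here for the over-time tests.
- Within-woman correlation ρ, assumed to be 0.3, 0.5 or 0.7. The documents give none.
- Equal variance σ² at the two visits, also assumed.

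**Group effect averaged over the two visits.** The mean of a woman's two scores has variance σ²(1+ρ)/2. Treated as independent rows, it is taken to be σ²/2. The naive standard error is therefore 1/√(1+ρ) of the correct one, and

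type I error = 2 × [1 − Φ(1.96/√(1+ρ))].

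**Group-by-time effect.** A woman's change between visits has variance 2σ²(1−ρ). Treated as independent, it is taken to be 2σ². The naive standard error is 1/√(1−ρ) times the correct one, and

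type I error = 2 × [1 − Φ(1.96/√(1−ρ))].

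| | ρ = 0.3 | ρ = 0.5 | ρ = 0.7 |
|---|---|---|---|
| Naive/correct SE, group | 0.877 | 0.816 | 0.767 |
| 1.96/√(1+ρ) | 1.719 | 1.600 | 1.503 |
| **Type I error, group** | **8.6%** | **11.0%** | **13.3%** |
| Naive/correct SE, group-by-time | 1.20 | 1.41 | 1.83 |
| 1.96/√(1−ρ) | 2.343 | 2.772 | 3.578 |
| **Type I error, group-by-time** | **1.9%** | **0.6%** | **0.03%** |

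**Check by simulation.** Ordinary least squares on stacked rows, 23 per group, 10,000 null runs, gave 8.3%, 10.7% and 13.7% for group and 2.1%, 0.8% and 0.1% for group-by-time. The formulas do not involve the sample size, so going to 60 per group does not help.

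**Does baseline EPDS as a covariate cure it?** Only in part. With the same ρ among all three visits, the residual correlation is ρ/(1+ρ) = 0.23, 0.33 and 0.41. Using these in the first formula gives a group type I error of 7.7%, 9.0% and 9.9%.

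**Analyses with one row per woman.** Simulated type I error for the 6-week score alone was 5.0%, 5.1% and 5.0% (12,000 runs). For the change between the two postpartum visits it was 4.9%, 5.0% and 5.0%. Both hold their level.

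**Precision available at 6 weeks.** Adjusting the 6-week score for baseline multiplies the residual variance by 1−ρ²: 1 − 0.09 = 0.91, 1 − 0.25 = 0.75 and 1 − 0.49 = 0.51, apart from the one degree of freedom spent.

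**The case against.** The strongest reply is that this is an unspecified method and not a demonstrated error. The SAP does not say that scores will be stacked as independent rows. Its sentence also fits a separate regression at each visit, a regression of change scores, or loose wording for a linear mixed model. That stands. Every error rate above is conditional on one reading. What remains is that the SAP does not choose between readings with different error rates, and that the method it names is invalid under one literal reading.

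It is also fair to say that the stakes are low. The trial is a pilot at 10% of the full sample, it gathers recruitment and crossover rates to settle a protocol, and the over-time analysis is secondary. That stands too, and it limits the weight of the point.

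Three stronger readings may tempt a reader, and the documents do not support them.

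- *The primary result is compromised.* It is not. It concerns one score per woman at 6 weeks, and regression of that score on group holds 5% with or without baseline adjustment.
- *A real treatment difference in trajectory would be missed with some known loss of power.* The SAP names no group-by-time test, plans for no such effect and sets no power for one. A power figure would need a benchmark from outside the documents.
- *The hourly labor pain scores suffer the same fault, and worse.* The protocol does record them ("Throughout labor, pain will be assessed hourly using 100mm visual analog scales for both pain intensity and pain unpleasantness"), but the SAP says only that pain will be analyzed. Pain is also measured by BPI at single visits. Nothing says that raw hourly rows enter any test, so no error rate can be attached.

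**Conclusion.** The point holds as a gap in specification with a real risk attached. EPDS is measured repeatedly in each woman, the SAP names only linear regression for its course, and no method for within-woman correlation is given.

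If the two postpartum scores were pooled as independent rows, the group test would reject roughly 1.7 to 2.7 times as often as its nominal level (8.6/5 to 13.3/5), and the group-by-time test well below it. The sizes rest on assumed correlations of 0.3 to 0.7, equal variances and that one reading of the text. They illustrate the risk and do not estimate what the trial will do. The effect is confined to secondary results of a pilot. The point is worth correcting because correction costs almost nothing, with moderate confidence given the ambiguity of the wording.

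**What to change.** **EPDS over time.** In the Statistical Analysis Plan, replace linear regression with a linear mixed model of the 6-week and 3-month EPDS. Include treatment, visit, treatment-by-visit and baseline EPDS as a covariate, with correlated errors within woman. GEE, ordinary regression with standard errors clustered by woman, or a separate baseline-adjusted regression at each visit would also be valid. The SAP should name one in advance.

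**EPDS at 6 weeks.** Keep this as the separate primary analysis and add baseline EPDS as a covariate in the linear regression. This is a gain in precision and not the correction of an error.

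**Cost.** A few sentences of SAP wording and a little more analysis work. No new data are needed, since baseline EPDS is already collected, and the sample size does not change.

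### The SAP does not specify baseline EPDS as a covariate in the 6-week EPDS comparison; adding it, with a rule for missing baselines, would probably narrow the confidence interval at almost no cost

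*Combined protocol and SAP*

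**What the plan says.** **Outcome.** The Study Protocol states: "At 6 weeks, we will measure the primary outcome of EPDS score". The Statistical Analysis Plan words it differently: "The primary outcome is risk for PPD, measured by EPDS score at the 6-week postpartum visit".

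**Model.** The only sentence on EPDS and treatment is "Linear regression will be used to examine the relationship between EPDS scores and treatment group, both over time in participants and by group". No covariate is named. The measures that the Study Protocol calls covariates (such as pain, perceived stress and attachment) are all taken after randomisation, and baseline EPDS is not among them.

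**Baseline.** The BASELINE paragraph reads "At the first encounter, an assessment will include measurements of depression (EPDS), anxiety (STAI inventory), resiliency (ER 89" and goes on to further scales. Women approached in early labor are covered too: "These women will answer the aforementioned baseline surveys but will not participate in QST".

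**Allocation.** It is revealed after that first encounter: "At the moment of patient request for labor epidural analgesia, one sealed and opaque envelope containing the next assignment group will be opened".

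**Missing data.** The one rule concerns follow-up: "Should a participant not respond to follow-up surveys at the specified time, we will exclude their data from analysis", with imputation held in reserve. Nothing addresses a missing baseline EPDS. Nothing requires an early-labor recruit to finish the baseline survey before her envelope is opened.

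**The concern.** The plan collects a pre-allocation measurement of its own primary outcome and does not say how it enters the 6-week comparison. If baseline predicts the 6-week score, leaving it out gives a wider interval than the data could support.

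The over-time wording does not settle this. It may bring baseline in as a time point, but it does not define the 6-week contrast, and the possible models differ in precision.

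A model that uses baseline also needs a rule for women without one. Dropping them can use up much of the gain.

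Validity is not in question. What could be lost is precision in the pilot's EPDS score estimate.

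**Working it through.** **Inputs from the documents.** Pilot target 23 per group, maximum 60 per group, attrition 15% (stated for the full trial).

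**Assumptions.** The baseline to 6-week correlation r is not given; 0, 0.3, 0.5 and 0.7 are shown. The number of missing baselines is not given; 2 of 23 (or 5 of 60) per group, missing at random, is used for illustration.

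**1. The plan's own figure.** For 20% v 10%, two-sided 5%, 80% power, with unpooled variance:

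n = (1.960 + 0.842)² × (0.20 × 0.80 + 0.10 × 0.90) / 0.10² = 196.2, so 197 per group.

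This matches the SAP. The full-trial size thus rests on a binary rate, and covariate adjustment of the score does not change it.

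**2. Adjusted v unadjusted CI width.** With nₐ per group in the adjusted model and n in the unadjusted one, the expected ratio is

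sqrt[(1 − r²) × (1 + 1/(2nₐ − 4)) × (n/nₐ)] × t(0.975, 2nₐ − 3) / t(0.975, 2n − 2).

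Example, nₐ = n = 23 and r = 0.5: sqrt(0.75 × 43/42) × 2.0167/2.0154 = 0.877, or 12% narrower.

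| Per group, no missing baseline | r = 0 | 0.3 | 0.5 | 0.7 | Break-even r |
|---|---|---|---|---|---|
| 20 (23 × 0.85 = 19.6, if 15% attrition applied to the pilot) | 1.015 | 0.968 | 0.879 | 0.725 | 0.170 |
| 23 | 1.012 | 0.966 | 0.877 | 0.723 | 0.157 |
| 60 | 1.004 | 0.958 | 0.870 | 0.717 | 0.093 |

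At 23 per group the unadjusted half-width is 0.594 SD. Adjusted, it is 0.574 SD at r = 0.3 and 0.521 SD at r = 0.5. The r = 0.5 gain is worth about 30% more participants (1/0.877² = 1.30).

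In 20,000 simulated trials per setting at 23 per group, the adjusted interval was the narrower one in 50% of trials at r = 0.2, 74% at r = 0.3 and 98% at r = 0.5.

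**3. Missing baselines.** The complete-case rows use the same formula. Example, 21 v 23 at r = 0.3: sqrt(0.91 × 39/38 × 23/21) × 2.0227/2.0154 = 1.015. The mean-imputation rows come from 10,000 simulated trials per setting; 95% CI coverage was 94.7% to 95.2%.

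| Handling, ratio to unadjusted | r = 0 | 0.3 | 0.5 | 0.7 |
|---|---|---|---|---|
| Complete case, 21 v 23 | 1.064 | 1.015 | 0.922 | 0.760 |
| Overall-mean imputation, 2 of 23 missing | 1.013 | 0.971 | 0.891 | 0.754 |
| Complete case, 55 v 60 | 1.050 | 1.002 | 0.910 | 0.750 |
| Overall-mean imputation, 5 of 60 missing | 1.004 | 0.962 | 0.882 | 0.746 |

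Dropping 2 of 23 per group raises break-even r from 0.157 to 0.342. Mean imputation keeps most of the gain.

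**4. Models with baseline as a time point.** Ratio of the CI to the unadjusted 6-week CI (large sample, equal SDs, complete data):

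| Model | r = 0.3 | 0.5 | 0.7 |
|---|---|---|---|
| Group means free at each time, 6-week contrast | 1.00 | 1.00 | 1.00 |
| Group-by-time contrast from baseline (change score), sqrt[2(1 − r)] | 1.18 | 1.00 | 0.77 |
| Baseline means held equal between groups, sqrt(1 − r²) | 0.95 | 0.87 | 0.71 |

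Of these, only the last matches covariate adjustment.

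**The case against.** **The over-time wording may already use baseline.** EPDS is measured at baseline, 6 weeks and 3 months, and a regression of both follow-up scores with baseline as a covariate would also fit the sentence. This stands so far: the plan does not exclude baseline; it does not specify its use. Since the models that fit the sentence run from an interval wider than the unadjusted one to the full gain, the choice should be written down.

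**It is a pilot with no precision target.** At r = 0.3 the half-width goes only from 0.594 to 0.574 SD, which alters no decision the plan describes. This stands, and it is why the point ranks low.

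**r is unknown.** Baseline is taken in the third trimester for some women and in early labor for others, so r may differ by route. At r = 0.2 the expected narrowing at 23 per group is under 1% (ratio 0.992). This also stands, but the worst case shown costs about 1%, so the balance favours adjusting.

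**Missing baselines are hypothetical.** The written sequence puts the survey first, and 2 of 23 is only an illustration. Even so, no rule exists, and early labor is a setting in which a survey may be left unfinished.

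**The endpoint may be binary.** The SAP speaks of risk for PPD and sizes the full trial on a proportion. The percentages here do not carry over to a binary rate. They do apply to the linear regression of scores that the SAP plans.

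**Conclusion.** The point holds as a low-severity precision gain. The SAP does not specify baseline EPDS as a covariate for the 6-week score comparison and has no rule for a missing baseline.

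At the pilot target, adjustment pays once r exceeds about 0.16. It narrows the interval by 3% to 28% for r between 0.3 and 0.7. The conclusion that a gain is probable rests on r lying above break-even, which the documents can neither confirm nor rule out. It also rests on the outcome being analysed as a continuous score and on baseline being recorded before allocation is known. The unadjusted analysis remains unbiased.

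**What to change.** In the Statistical Analysis Plan:

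- State the primary model as 6-week EPDS score = treatment + baseline EPDS, reporting the adjusted mean difference with its 95% CI.
- Keep every randomised woman who has a 6-week score. Where baseline EPDS is missing, or was completed after the envelope was opened, substitute a simple imputed value such as the overall baseline mean, not calculated by group.
- Make the over-time analysis (baseline, 6 weeks, 3 months) secondary.

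The cost is SAP wording and one degree of freedom, with a CI about 1% wider at 23 per group if r is near zero. No new data are collected and no study procedure changes.

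### The SAP states no adjustment for the pain-EPDS regression, although pain is not randomized and baseline EPDS and catastrophizing scores are already collected

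*Combined protocol and SAP*

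**What the plan says.** The Statistical Analysis Plan describes two analyses of EPDS. The first is the treatment comparison: "Linear regression will be used to examine the relationship between EPDS scores and treatment group, both over time in participants and by group". The second is the analysis at issue: "The relationship between pain and EPDS will also be examined using linear regression". The second sentence lists no covariates, and does not say which pain measure or which EPDS time point is meant.

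The Study Protocol section offers several candidates for pain. During labor, "pain will be assessed hourly using 100mm visual analog scales for both pain intensity and pain unpleasantness". The Brief Pain Inventory (BPI) short form is given within two days of delivery, at 6 weeks and at 3 months. EPDS is taken at baseline, 6 weeks (primary) and 3 months.

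At baseline, "an assessment will include measurements of depression (EPDS), anxiety (STAI inventory), resiliency (ER 89), pain catastrophizing (PCS), perceived social support (MSPSS) and pain (BPI-long form". Women approached in early labor answer the same surveys and miss only the quantitative sensory testing, so baseline EPDS and PCS are planned for everyone. No model in the SAP uses them.

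The protocol applies the word covariate to later measures only. After delivery: "Within 2 days we will measure co-variates of pain (BPI short), breastfeeding (yes/no) and perceived stress (PSS". At 6 weeks, the team measures the "primary outcome of EPDS score as well as co-variates including pain (BPI short", followed by attachment (MPAS), parenting self-efficacy (PMP-SE), child development (ASQ-3) and breastfeeding.

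**The concern.** Randomization protects the comparison of CSE with epidural. It does not protect a regression of EPDS on pain, because women are not assigned their pain. A woman who starts with low mood or a tendency to catastrophize may report more pain and also score higher on EPDS six weeks later. An unadjusted slope then appears even if pain does nothing to mood, and the data needed to reduce the problem are already in hand.

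Two features make a misreading more likely. If the pain measure is the 6-week BPI, it is collected at the same contact as the primary EPDS, so direction cannot be inferred. And an analyst looking in the protocol for an adjustment set finds the label attached only to variables measured after randomization. Those leave baseline vulnerability unadjusted here, and in the EPDS-by-group model they could absorb or distort part of the treatment effect.

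At stake is the interpretation of one of the two named EPDS analyses, in a pilot meant to precede a full trial.

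**Working it through.** **The plan's own figure.** The SAP gives no sample size or power for the pain-EPDS regression. Its only power figure, 197 per group, is for the group comparison. It reproduces for 20% versus 10% with unpooled variance: (0.2×0.8 + 0.1×0.9) × (1.960 + 0.842)² / 0.10² = 196.2, rounded up to 197. It has no bearing on this point.

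**Inputs.**
- From the SAP: n = 46 (23 per group), with a ceiling of 120 (60 per group). The SAP's 15% attrition figure would leave 46 × 0.85 ≈ 39 women.
- Assumed, because the documents give no correlations: one baseline factor (depression or catastrophizing) has correlation *b* with later EPDS and *a* with pain; pain has no direct effect on EPDS; two-sided 5% test.

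**Step 1: correlation produced by the common cause alone.** r = a × b.
- Mild: 0.2 × 0.4 = 0.08
- Middle: 0.3 × 0.5 = 0.15
- Strong: 0.4 × 0.6 = 0.24

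**Step 2: chance that the unadjusted slope is significant.** By the Fisher z approximation, the test statistic is centred at atanh(r) × √(n − 3), and √43 = 6.557 at n = 46.
- r = 0.08: 0.0802 × 6.557 = 0.53, giving about 8%
- r = 0.15: 0.1511 × 6.557 = 0.99, giving about 17%
- r = 0.24: 0.2448 × 6.557 = 1.61, giving about 36%

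Simulation with ordinary least squares agrees:

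| baseline-pain / baseline-EPDS | n = 46 | n = 39 |
|---|---|---|
| 0.2 / 0.4 | 8.2% | 7.8% |
| 0.3 / 0.5 | 17.1% | 14.6% |
| 0.4 / 0.6 | 36.5% | 31.8% |

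A larger pilot makes this worse: the middle setting gives about 37% at n = 120.

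**Step 3: after adjustment.** With the baseline factor and treatment group in the model, simulated rejection is about 5% in every setting tried. This assumes that the covariate captures the common cause fully.

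**Step 4: how much comes from omitting treatment group.** Suppose group is the only omitted common cause and shifts pain and EPDS equally by *d* SD. Then r = (d²/4) / (1 + d²/4).
- d = 0.3: 0.0225 / 1.0225 = 0.02; rejection 5% at n = 46
- d = 0.5: 0.0625 / 1.0625 = 0.06; rejection 7%
- d = 0.8: 0.16 / 1.16 = 0.14; rejection 15%

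Group matters little unless it shifts both variables strongly.

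**Step 5: cost of adjustment.** At n = 46, intercept, pain and three covariates leave 46 − 5 = 41 residual degrees of freedom, against 44 for pain alone.

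**The case against.** The strongest reply is that the SAP promises only to examine a relationship. If baseline mood drives both variables, pain and EPDS really are correlated, and finding that is power, not error. This stands as a limit on the numbers: 8% to 36% are false-positive rates only for a direct effect of pain. It does not rescue the analysis, because a correlation that baseline vulnerability could wholly explain tells the investigators little about pain.

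Four stronger readings are tempting, and the documents do not support them.

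- *The SAP rules out adjustment.* It is silent. It never calls the model unadjusted, and the protocol says of the sensory testing that "we will determine the participant's sensitivity profile which we will use in our study analysis", so the SAP's one-line descriptions are not a complete list of model terms.
- *Pain is the trial's stated path from technique to depression.* A reader may infer this from the design, but no mediation hypothesis is written down, and nothing makes the full trial depend on this slope.
- *Omitting treatment group is the main fault.* Step 4 shows that it is a minor contributor.
- *Post-randomization variables are planned adjusters in the EPDS-by-group model.* The SAP names no covariates there, and it lists pain, attachment, infant development and breastfeeding among the variables to be compared with treatment group, which treats them as outcomes. The covariate label in the protocol may be loose wording. It still needs a clarifying sentence.

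It is also fair to say that anxiety, social support and baseline pain are measured too, so a short adjustment set leaves some confounding behind.

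**Conclusion.** The point holds as a gap in pre-specification with a predictable consequence. The only description of the pain-EPDS regression states no adjustment, and baseline EPDS and PCS are available for all women. Run as written, the slope cannot separate a pain effect from pre-existing vulnerability. Under the assumed correlations and no direct pain effect, it would be significant in about 8% to 36% of pilots at n = 46, against about 5% after adjustment. The correlations are assumptions, and the 5% depends on the baseline scores capturing the common cause. Adjustment reduces measured confounding but does not make the association causal. The randomized comparison of EPDS by group is not affected, provided that post-randomization measures stay out of it. The change is worth making because it is nearly free.

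**What to change.** Replace the SAP sentence with wording such as:

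> The association between labor pain (one pre-named summary per woman of the hourly VAS) and 6-week EPDS will be estimated by linear regression adjusting for baseline EPDS and baseline PCS, with treatment group included, and reported as an exploratory association with a 95% CI.

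The labor VAS is one reasonable choice. What matters is that a single measure is named in advance and precedes the EPDS it is meant to explain. The SAP should say whether intensity or unpleasantness is used and which readings enter the summary.

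Add two sentences:
- BPI and EPDS taken at the same visit are analysed as cross-sectional only.
- BPI, PSS, breastfeeding, MPAS, PMP-SE and ASQ-3 measured after randomization are not adjustment variables in the EPDS-by-group model.

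The cost is SAP wording and three degrees of freedom at n = 46, with no new data. Residual confounding remains and should be acknowledged when the result is reported. Adding many more baseline scores would strain a sample of this size, so the set should stay short.
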